Record pulmonary rehab				X	X	X		
IRT	X	X ⁵	X					
Adverse events, concomitant treatments		X	X	X	X	X	X	X
Conclude subject participation								X

* Informed consent needs to be signed before any procedure related to the study, all AEs and Concomitant Treatments occurring after the Informed consent have to be recorded.

¹ HRCT will be acceptable if done within 24 months, if not available patient will be sent for HRCT between Visit 1 and 2, or within 7 days of completing Visit 2.

² Patients will wear the physical activity monitor and complete the eDiary (PROactive Tool) 24 hours every day for 1 week prior to Visits 1, 2, 5 and 7. Devices will be dispensed in clinic at Visits 0 and 1, and will be shipped to patient or picked up from clinic at least 1 week prior to Visits 5 and 7.

³

exercise testing center. The incremental and practice tests can both be done at Visit 1.

⁵ Access IRT to terminate if screen fail at Visit 1 or between Visit 0 and Visit 1.

- ⁶ Time between visits 2 and 3 may be extended for up to 6 weeks to allow scheduling of the onset of pulmonary rehabilitation, the treatment period will begin on the first day of pulmonary rehabilitation and all visits move accordingly to keep the same visit schedule.
- ⁷ Height and weight to be collected at Visit 1 only.

TABLE OF CONTENTS

TITLE PAGE	1
CLINICAL TRIAL PROTOCOL SYNOPSIS	2
FLOW CHART	6
TABLE OF CONTENTS	8
ABBREVIATIONS	12
1. INTRODUCTION.....	15
1.1 MEDICAL BACKGROUND.....	15
1.2 DRUG PROFILE	15
1.3 RATIONALE FOR PERFORMING THE TRIAL	15
1.4 BENEFIT - RISK ASSESSMENT.....	16
2. TRIAL OBJECTIVES AND ENDPOINTS.....	17
2.1 MAIN OBJECTIVES, PRIMARY AND SECONDARY ENDPOINTS.....	17
2.1.1 Main objectives.....	17
2.1.2 Primary endpoint(s).....	17
2.1.3 Secondary endpoint(s)	17
3. DESCRIPTION OF DESIGN AND TRIAL POPULATION.....	19
3.1 OVERALL TRIAL DESIGN AND PLAN	19
3.2 DISCUSSION OF TRIAL DESIGN, INCLUDING THE CHOICE OF CONTROL GROUP(S)	19
3.3 SELECTION OF TRIAL POPULATION	19
3.3.1 Main diagnosis for trial entry	20
3.3.2 Inclusion criteria	20
3.3.3 Exclusion criteria	21
3.3.4 Withdrawal of patients from therapy or assessments	21
3.3.4.1 Withdrawal from trial treatment	22
3.3.4.2 Withdrawal of consent for trial participation.....	22
3.3.4.3 Discontinuation of the trial by the sponsor	22
4. TREATMENTS.....	24
4.1 INVESTIGATIONAL TREATMENTS	24
4.1.1 Identity of the investigational medicinal products.....	24
4.1.2 Selection of doses in the trial.....	24

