5.1.2.4 Daily activity monitoring

Daily activity monitoring will be conducted using the Dynaport device between Visits 0 and 1, 1 and 2 and for 7 days prior to Visits 5 and 7 (End of Treatment - EOT). The device will be dispensed to the patient via either picking up at the office or sent via commercial shipping to the patient in advance of the scheduled start date. The patient will wear the device for 7 consecutive days, 24 hours a day, between or prior to the scheduled visits and bring the device with them to the visit. The information will be downloaded by the investigator at the scheduled visit. Further information and instructions for the activity monitoring will be provided in the ISF.

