6. INVESTIGATIONAL PLAN

6.1 VISIT SCHEDULE

This trial consists of two parts, a screening and an interventional period. The screening period consists of the time between signing consent and randomization, and will last a minimum of 7 days. The interventional period consists of the time from randomization through the week 24 assessment visit.

There are two screening visits (Visit 1, which must be preceded by a separate informed consent Visit 0) and 6 visits (Visits 2 to 7) planned within the 24 week interventional period. There is no follow up period in this trial.

After giving his/her informed consent, the patient will be screened for inclusion (see [Section 3.3.2](#) and exclusion criteria (see [Section 3.3.3](#)) for the trial at Visits 0, 1 and Visit 2 (refer to [Flowchart](#)).

The patient will be dispensed an activity monitor and ProActive tool (eDiary) at the consent visit, and will wear the activity monitor and use the eDiary for 7 days prior to Visit 1 for training purposes.

Visit 2 can be performed once the results from local laboratory of Visit 1 are obtained and the patient has worn the activity monitor and completed the eDiary for 7 days. If for any reason the screening phase for an individual patient lasts for more than 6 weeks, then the laboratory examination for Visit 1 has to be repeated before randomization. The patient will be randomized at Visit 2 if all inclusion and none of the exclusion criteria are fulfilled. Central HCRT is not required prior to randomization, but if historical HRCT is not available to be sent for central calculation of QLF, a scan should be obtained after screening/consent at the latest 7 days after Visit 2.

On treatment visits will be performed at 3, 6, 12, 18 and 24 weeks. Procedures for these visits are outlined in the flow chart and detailed instructions are available in [Section 5](#), select appendices and the ISF, as applicable.

Visit 7 is the end of treatment visit, there is no follow up period. Visit 7 procedures should be followed for early termination visits if possible.

If a patient misses a visit, the visit should be rescheduled as soon as possible. If unable to reschedule, the clinical monitor should be contacted.

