6.7 BASELINE, TIME WINDOWS AND CALCULATED VISITS

As a general rule, last assessment before treatment period start (included) will be used as baseline. For patients randomized to the Non-Pulmonary Rehabilitation group treatment period starts from randomization. For patients randomized to the Pulmonary Rehabilitation group treatment period starts from first day of pulmonary rehabilitation. If the baseline value is missing and the screening value is available, then the baseline value will be defined as the screening value taken closest to baseline date.

A windowing will be performed in order to assign data to the relevant study visit based on the actual day of the assessment. If after windowing of visits at baseline, two values fall within the same baseline interval, then the last value will be taken into account. If after windowing of

post-baseline visits, two visits fall in the same interval, then the measurement closest to the planned visit will be taken into account. In case two measurements are equidistant from the planned visit, then the last one will be picked.

Time windowing rules for physical exam, vital signs, and laboratory tests:

Time window of actual day			Allocated to		
Start day	End day (included)	Length of the time-window [days]	Visit number	Visit name	Planned day of the visit
-	1	-	2	Baseline	1
2	32	31	3	3 weeks	22
33	63	31	4	6 weeks	43
64	105	42	5	12 weeks	85
106	147	42	6	18 weeks	127
148	-	-	7	24 weeks	169

Time windowing rules for spirometry, six minutes walk test, [REDACTED], PROactive tool, SGRQ, KBILD, UCSD SOBQ:

Time window of actual day			Allocated to		
Start day	End day (included)	Length of the time-window [days]	Visit number	Visit name	Planned day of the visit
-	1	-	2	Baseline	1
2	126	125	5	12 weeks	85
127	-	-	7	24 weeks	169

Include for analysis and in average calculation of the ProActive tool scores the following measurements. If a patient does not have at least 5 days of measurements available, no score is calculated (except for baseline, noted below).

- Baseline = 7 days before and up to actual Visit 2 (excluded). If a patient does not have at least 5 days of measurements within this time window, then use 7 days before and up to actual Visit 1 (excluded) (only if 5 days of measurements are available)
- 12 weeks = 7 days before and up to actual Visit 5 (excluded)
- 24 weeks = 7 days before and up to actual Visit 12 (excluded)

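### SAP 6.7 counts activity days back from the actual visit and has no fallback after baseline, so a complete 7-day recording can be discarded if the visit moves 3 or more days late and wear is not extended or repeated

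*SAP*

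**What the plan says.** **Selection rule (SAP 6.7).** The week-12 days are defined as "12 weeks = 7 days before and up to actual Visit 5 (excluded". The week-24 line reads "24 weeks = 7 days before and up to actual Visit 12 (excluded". The minimum is stated as: "If a patient does not have at least 5 days of measurements available, no score is calculated". Only baseline has a second choice: if the week before Visit 2 holds too few days, "then use 7 days before and up to actual Visit 1 (excluded", provided 5 days are available there.

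**Allocation table (SAP 6.7).** The same section lists the PROactive tool in a table of day windows. Its 12-week row is "2 126 125 5 12 weeks 85" (start day, end day, length, visit number, visit name, planned day). Day 127 onward goes to Visit 7, 24 weeks.

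**Wear (protocol).** The Flow Chart footnote on the monitor has it worn "24 hours every day for 1 week prior to Visits 1, 2, 5 and 7". Section 5.1.2.4 says: "The patient will wear the device for 7 consecutive days, 24 hours a day, between or prior to the scheduled visits". It leaves further instructions to the investigator site file. Section 6.1 describes the week before Visit 1 as training.

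**Visit timing (protocol).** The Flow Chart allows ±3 days at Visit 5 (day 85) and ±7 days at Visit 7 (day 169). Section 6.1 adds: "If a patient misses a visit, the visit should be rescheduled as soon as possible". No text in the two documents says whether wear is extended or repeated when a visit moves.

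**The concern.** The recording and the selection window can separate. The recording is a fixed block of 7 days once the patient has finished wearing the device. The selection window moves with the visit. If the visit is postponed after wear has begun, the overlap shrinks day for day, and the 5-day minimum turns a modest delay into a missing score. The recording still exists, and it lies within the days that the SAP's own table assigns to that time point.

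The endpoint at stake is change from baseline in daily accelerometer activity at 12 and 24 weeks, a secondary endpoint (protocol 2.1.3, SAP 5.2.2). SAP 6.6 prescribes observed cases without imputation, so a discarded recording simply drops out. At baseline the effect differs: a usable week can be replaced by an earlier training week, and both later changes are then measured from it.

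**Working it through.** The plan gives no figure to reproduce. This is a day count.

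**Inputs**
- Planned days: Visit 5 = 7 × 12 + 1 = 85; Visit 7 = 7 × 24 + 1 = 169 (both match the Flow Chart).
- Permitted delay: up to +3 at Visit 5 and +7 at Visit 7.
- Recording: 7 consecutive days. If it ends on the eve of the planned visit, it covers days 78–84 or 162–168.
- SAP window: V − 7 to V − 1, where V is the actual visit day.
- Minimum: 5 days.
- The SAP's Visit 12 is read as Visit 7. Protocol 6.1 ends the visits at 7, and the SAP's own table puts 24 weeks at Visit 7.

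**Formula.** Let s be the delay in days, and g the number of days between the end of the recording and the eve of the planned visit. With no extension or repeat of wear, days kept = max(0, 7 − s − g).

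**Recording ending on the eve of the planned visit (g = 0)**

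| Delay s | 0 | 1 | 2 | 3 | 4 | 5 | 6 | 7 |
|---|---|---|---|---|---|---|---|---|
| Days kept | 7 | 6 | 5 | 4 | 3 | 2 | 1 | 0 |
| Score | yes | yes | yes | no | no | no | no | no |

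Example: days 78–84 are worn and Visit 5 is held on day 88. The window is days 81–87, the overlap is days 81–84, and 4 is below 5. At Visit 5 only +3 is affected, 1 of the 7 permitted days. At Visit 7 it is +3 to +7, 5 of the 15 permitted days. At +2 a score survives only if all five remaining days are valid.

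**Other start days.** The device reaches the patient at least a week ahead, and the exact start day is not fixed. With g = 1, 2 or 3, the recording is lost from a delay of +2, +1 or 0 days.

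**Wear extended to, or moved with, the visit.** 7 days are kept at every permitted delay, and nothing is lost.

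**Early visits.** A visit 3 days early also leaves 4 days, but that recording was cut short. It is a different case.

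**Baseline.** With the actual Visit 2 as V, a week ending g days before the eve of Visit 2 keeps 7 − g days. At g = 3 that is 4, so the rule turns to the week before Visit 1. Such a gap is possible: section 5.1.2.4 places this wear only between Visits 1 and 2, and section 6.1 has Visit 2 wait for laboratory results and foresees screening of more than 6 weeks.

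**The case against.** The strongest objection is that the protocol ties wear to the visit, as the SAP does. The Flow Chart footnote and sections 5.1.2.4, 6.2.1 and 6.2.2 all speak of 7 days before the visit. The word scheduled in 5.1.2.4 can simply mean the protocol visits, not a fixed calendar date. A Visit 5 booked from the outset for day 88 would have wear on days 81–87 and lose nothing. Patients bring the device to the visit, so they may still be wearing it, and the site file may cover postponed visits. All of this stands. The loss needs a visit that moves late after wear has begun, with no extension or repeat.

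A second objection is that the wide table assigns data to time points, while the 7-day rule chooses which days to average. The two are therefore not in direct contradiction, and the single-assessment measures in that table are not a fair comparison. This also stands. The table shows only that the SAP would regard the recording as belonging to the time point.

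A third is that little depends on it. SAP section 4 limits the secondary endpoints to description after the trial's termination, and the primary 6-minute walk endpoint is untouched. That bounds the impact but does not remove the defect. Visits may move, no text in the two documents requires re-wear, and weeks 12 and 24 have no fallback.

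**Conclusion.** The point holds conditionally. With a recording timed to the planned date and not extended or repeated, a delay of 3 days or more within the protocol's windows discards 7 complete days at week 12 or week 24. A valid week between Visits 1 and 2 that ends 3 or more days before the eve of Visit 2 is replaced by the training week.

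The documents do not support some stronger readings:
- **That any 3-day delay costs the score.** It does not if wear continued or moved with the visit.
- **A percentage of scores lost.** The documents do not say how often visits move after wear begins or how delays are distributed, so counts of permitted days are not loss rates.
- **That the remaining means favour fitter patients, or that the arms differ.** Postponement through illness is plausible, but nothing in the documents measures it.

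Two assumptions remain. The Visit 7 result depends on reading Visit 12 as Visit 7; taken literally, the line refers to no visit in this trial. The rule is worded for PROactive tool scores, so its application to the steps and VMU endpoint is an inference from the accelerometer note that closes SAP 6.7. The effect is confined to descriptive PROactive and accelerometer results.

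**What to change.** In SAP 6.7:
1. Keep the 7 days before the actual visit as first choice.
2. If they hold fewer than 5 valid days at 12 or 24 weeks, use the most recent 7-calendar-day span with at least 5 valid days that ends before the visit day (visit day excluded) and within a pre-specified limit, for example 14 days. Allocate it by the day windows already in that section.
3. At baseline, apply step 2 to the week recorded between Visits 1 and 2 before turning to the week before Visit 1.
4. Correct Visit 12 to Visit 7, and state whether the rule covers the steps and VMU scores.

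One detail is worth settling in step 2. In the day-88 example, the most recent qualifying span is days 80–86, which averages only days 80–84. Requiring the span to end on a valid recording day gives days 78–84 and uses all 7. At the longest permitted delay (Visit 7 on day 176), the recording ends on day 168, 176 − 168 = 8 days earlier, inside a 14-day limit. The limit itself is a choice for the sponsor.

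If the site-file instructions already require wear to be extended or repeated, citing them in the SAP would largely settle the week-12 and week-24 part.

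The cost is a few lines of SAP text and a small programming change, with no new data. The downside is that some recordings will end several days before the visit; the number using the fallback should be reported by arm and time point.

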5.1.2.6 PROactive tool

In this trial, the PROactive tool (D-PPAC) together with the activity monitor will be used to collect the PROactive item scores. The D-PPAC consists of 9 items in total: 7 items filled out on an electronic interface (eDiary) and 2 items to be obtained from the activity monitor (see [Appendix 10.4](#)) The items on the eDiary will be completed by the patient at home every day for 7 days before Visits 1, 2, 5, and 7 (EOT). Patients will receive a leaflet with detailed instructions on how to use it, as well as being given a demonstration at the study site.

Data from the eDiary for each period will be uploaded to the vendor's database, and subsequently transferred to the trial database.

The eDiary and the activity monitor data will be uploaded to the trial database for use in calculating the domain scores and PROactive total and domain scores.

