5.2.2 Secondary endpoints

[figure not shown]
The secondary endpoints are:

[figure not shown]
- Change from baseline in Quality of Life (QoL) (SGRQ, KBILD, UCSD-SOBQ) at 12 and 24 weeks
- Change from baseline in 6MWT distance at 24 weeks
- Change from baseline in Forced Vital Capacity (FVC) at 12 weeks and 24 weeks using each of
 - Absolute change from baseline of FVC and FVC % predicted
 - Relative change from baseline of FVC and FVC % predicted
 - Absolute categorical change of FVC % predicted (decrease by >5%, increase by >5%, and change within ≤ 5%)

- Absolute categorical change of FVC% predicted (decrease by >10%, increase by >10%, and change within $\leq 10\%$)
- Change from baseline in daily accelerometer activity from baseline at 12 and 24 weeks
 - Score of average Steps/day
 - Score of average VMU/day

Refer to Section 6.7 for baseline value definition. Refer to Section 6.6 for missing baseline assessment.

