Note: For accelerometer scores, if a patient has more than one record for a given day, the record will not be used for calculation. For eDiary scores, if a patient has more than one record for a given day, the worse answer will be used for calculation.

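### SAP 6.7 ends the 24-week averaging window for the PROactive tool scores at a Visit 12 that does not exist in this trial; Visit 7 is meant

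*SAP*

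**What the plan says.** SAP 6.7 lists the days that enter the average for the PROactive tool scores. Baseline uses the week before Visit 2, with the week before Visit 1 as a fallback. The 12-week value uses the week before Visit 5. The 24-week rule is "24 weeks = 7 days before and up to actual Visit 12 (excluded"). The same paragraph sets a minimum amount of data: "If a patient does not have at least 5 days of measurements available, no score is calculated", with an exception for baseline only. A note under the list gives a rule for duplicate records, beginning "For accelerometer scores, if a patient has more than one record for a given day".

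Both windowing tables in SAP 6.7 assign 24 weeks to Visit 7, planned Day 169. The second table names the PROactive tool.

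Protocol 6.1 states "Visit 7 is the end of treatment visit, there is no follow up period". Protocol 5.1.2.4 schedules the activity monitor during screening and "for 7 days prior to Visits 5 and 7 (End of Treatment - EOT"). Protocol 5.1.2.6 schedules the eDiary items "every day for 7 days before Visits 1, 2, 5, and 7 (EOT"). Flow Chart footnote 2 has both devices in use "24 hours every day for 1 week prior to Visits 1, 2, 5 and 7".

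SAP 5.2.2 lists two accelerometer entries under the secondary endpoints. One is a score of steps per day and the other is "Score of average VMU/day".

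**The concern.** The sentence is operative: it determines which days of monitor and diary data form the 24-week value. It names a visit outside the trial's schedule, so it cannot be executed as written. A literal program would find no qualifying days and, under the five-day minimum, would return a missing score for every patient at 24 weeks. Unlike baseline, the 24-week window has no fallback.

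Change in daily accelerometer activity at 24 weeks is a listed secondary endpoint. If the window serves that endpoint too, its 24-week column depends on this line.

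**Working it through.** **1. Visit numbers and planned days.** Inputs: the treatment-phase visits in the Flow Chart and Protocol 6.1 (weeks 3, 6, 12, 18 and 24 for Visits 3 to 7). Planned day = 7 × week + 1.

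| Visit | Week | 7 × week + 1 | Day in SAP 6.7 |
|---|---|---|---|
| 3 | 3 | 22 | 22 |
| 4 | 6 | 43 | 43 |
| 5 | 12 | 85 | 85 |
| 6 | 18 | 127 | 127 |
| 7 | 24 | 169 | 169 |

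The SAP's own planned days are reproduced, and 24 weeks is Visit 7. Visits run from 0 to 7. Protocol 5.2.3 has another stray number (laboratory tests through Visit 9), but no available text defines a Visit 12.

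**2. Averaging rule against wear schedule.**

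| Time point | SAP 6.7 averaging rule | Wear scheduled in the protocol |
|---|---|---|
| Baseline, fallback | before Visit 1 | before Visit 1 |
| Baseline | before Visit 2 | before Visit 2 |
| 12 weeks | before Visit 5 | before Visit 5 |
| 24 weeks | before Visit 12 | before Visit 7 |

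Three of the four rows agree. The only wear period left for the 24-week row is the week before Visit 7.

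**3. Literal result.** With no Visit 12 there are 0 qualifying days for every patient. Since 0 < 5, no 24-week score is calculated.

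**4. Corrected result.** With Visit 7 on planned Day 169, the window starts at 169 − 7 = Day 162. The visit day is excluded, so it ends on Day 168. Days 162 to 168 are seven days and lie inside the 24-week interval of the windowing table that covers the PROactive tool (Day 127 onward).

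**5. Reach.** The list is introduced as governing the PROactive tool scores. Protocol 10.4.1 builds two monitor outputs, steps and VMU, into that instrument, and the SAP note beneath the list refers to accelerometer scores. Taken together, these suggest that the same windows serve the accelerometer secondary endpoint. The SAP does not say so outright.

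**6. The VMU label.** The protocol's abbreviation list expands VMU as already per minute. Protocol 10.4.1 gives the monitor output as VMU/min, and 10.4.2 heads the bands as a daily value in VMU/min, with six bands scored 0 to 5. The amount maximum agrees with this: 4 + 4 + 4 + 5 = 17, the figure in Protocol 10.4.1. On the protocol's definition, the SAP entry can be read as the average of a daily per-minute value, which is what the bands need. The label is loose, but it does not establish a different derivation.

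**The case against.** The strongest reply is that this is a self-evident slip. The line is itself labelled 24 weeks, the table above it names the PROactive tool and puts 24 weeks at Visit 7, and the protocol schedules wear before that visit. Only one reading is possible, and a careful programmer would reach it. This stands, and it limits the size of the point. It does not remove the point, because SAP section 3 presents the document as the detailed procedures for executing the analysis, and this rule cannot be executed as written.

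A second reply concerns reach. The rule is written for the PROactive tool scores, whose total and domain scores are not among the visible secondary endpoints, and SAP section 4 drops the further endpoints. This also stands in part: the link to a reported endpoint rests on the inference in step 5.

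A reader might go further and infer that the 24-week accelerometer data would be lost. The documents do not support that as a likely outcome, because the intended visit is plain from the same section.

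A reader might also infer from the VMU/day label that daily totals would be put through the per-minute bands, so that nearly everyone would score at the top. The documents do not support that either. No available text tells anyone to sum over the day, and the protocol's definition of VMU already contains the minute. SAP text missing from this copy may give the derivation: SAP 7.7 cites a Section 5.4.3 that is not shown, and the contents list goes from 5.2.2 on page 5 to Section 6 on page 9.

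**Conclusion.** The point holds for the visit number. SAP 6.7 contradicts its own windowing tables and the protocol, and as written it yields no 24-week score. It is a minor, editorial error. The primary endpoint is untouched, no hypothesis test depends on the rule, and SAP sections 4 and 7.5.2 limit the secondary endpoints to descriptive statistics after termination.

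The effect on the accelerometer secondary endpoint assumes that the PROactive windows apply to it, which the note in SAP 6.7 suggests but does not state. Days 162 to 168 assume that Visit 7 falls on its planned day; otherwise the window moves with the actual visit.

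The VMU wording is a request for clarification and not a demonstrated error.

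**What to change.** In SAP 6.7, replace Visit 12 by Visit 7 in the 24-week averaging rule, and add a sentence saying whether the same windows apply to the accelerometer scores in SAP 5.2.2. In SAP 5.2.2, describe the VMU entry as the score of the average daily VMU/min value, matching the bands in Protocol 10.4.2, unless SAP text not shown already does so.

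The cost is one changed word and two short clarifications. No new data, analysis or protocol change is needed.

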6.2.3 Follow up period and trial completion

- Visit 7/End of Treatment (EOT) or when the patient is discontinued
- Adverse events and concomitant therapy assessment since last visit

- Review pulmonary rehabilitation attendance with patient and record information from pulmonary rehabilitation reports into eCRF for patients in the PR treatment group (for patients discontinued during first 12 weeks)
- Physical examination including vital signs
- SGRQ, KBILD and UCSD SOBQ
- Collect and download/review PROActive Tool from eDiary and activity monitor data
- Resting SpO₂
- Resting 12-lead electrocardiogram
- Blood samples for laboratory tests
- Urinary pregnancy test (done locally)
- Pulmonary function test including FVC
- DL_{CO}
- Six minute walk test
- 
- End Of Treatment page to be completed

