4. CHANGES IN THE PLANNED ANALYSIS OF THE STUDY

In writing the core TSAP, these corrections were made to the specifications of the initial TSAP:

1. Important protocol deviation (IPD) E1 in Section 6.2 “No post-baseline 6 MWT assessments” was clarified to E1 “No post-baseline 6 MWD assessments at 12 weeks” and E2 “No baseline 6 MWD assessments” to reflect the primary outcome being measured at 12 week visit.
2. iPD D2 in Section 6.2 was changed from “Discontinued nintedanib” to “Discontinued nintedanib before 12 week visit” to reflect the primary outcome being measured at 12 week visit.
3. The Screening trial period in Section 6.1 was changed from “informed consent to randomization” to “first informed consent to randomization” to account for re-consenting of patients.
4. The trial periods defined in Section 6.1 was clarified to make the distinction between efficacy analysis and safety analysis.

Following termination of the trial, limited efficacy analysis will be performed for an abbreviated CTR. Primary and secondary endpoints will be limited to descriptive outcome measures. Further endpoints will not be done.

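### SAP 6.7 gives two unreconciled rules for dating activity scores, and the 24-week rule points to a visit that does not exist; correcting the number to Visit 7 alone would let early-termination recordings count as 24-week activity.

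*SAP*

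**What the plan says.** SAP 6.7 opens with a general principle: "A windowing will be performed in order to assign data to the relevant study visit based on the actual day of the assessment". Its second table, introduced as "Time windowing rules for spirometry, six minutes walk test, [REDACTED], PROactive tool, SGRQ, KBILD, UCSD SOBQ", has one row for 12 weeks ("2 126 125 5 12 weeks 85": days 2 to 126, 125 days long, Visit 5, planned day 85) and one for 24 weeks (day 127 onward, Visit 7, planned day 169). If two post-baseline visits fall in one window, the value nearer the planned day is used. If they are equally near, the later one is used.

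Below the table, the same section defines which daily measurements enter the PROactive averages. The 12-week average takes the 7 days before actual Visit 5. For the last time point the text is "24 weeks = 7 days before and up to actual Visit 12 (excluded". A score needs at least 5 days of measurements, with a fallback to Visit 1 for baseline only.

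The protocol has no Visit 12. Protocol 6.1 plans Visits 2 to 7 and adds: "Visit 7 procedures should be followed for early termination visits if possible". Protocol 6.2.3 describes the last visit as "Visit 7/End of Treatment (EOT) or when the patient is discontinued" and includes collection of eDiary and monitor data in it.

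SAP 5.2.2 lists scores for average steps and average VMU at 12 and 24 weeks among the secondary endpoints. SAP 4 limits the primary and secondary endpoints to descriptive outcome measures.

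**The concern.** Two instructions in one section apply to the same scores and can give different time points. A programmer has to choose, and the SAP gives no order of precedence. The visible error in the second instruction, Visit 12, will almost certainly be corrected to Visit 7. That correction brings the conflict into effect, because Visit 7 in this trial is both the week-24 visit and the visit held when a patient stops early.

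Protocol 2.1.1 asks whether the benefit of rehabilitation lasts after the 12-week course ends. The 24-week activity summary is part of that answer. A recording made before or around the end of the course, but labelled 24 weeks, does not bear on that question. It would also stand beside a 24-week walk and FVC summary built on a different definition of 24 weeks.

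**Working it through.** **Inputs.** The windows, planned days, tie-break, averaging rules and 5-day minimum are in SAP 6.7. The double role of Visit 7 is in Protocol 6.1 and 6.2.3. Monitor supply and wear are in the Protocol flow chart (footnote 2), 5.1.2.4 and 6.2.2.

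**1. The plan's own figures.** Window length = end − start + 1 = 126 − 2 + 1 = 125 days, as stated. The midpoint of the planned days is (85 + 169) / 2 = 127, which is the first day of the 24-week window. The table is internally consistent.

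**2. Literal reading.** Visit 12 never takes place, so no 7-day period ends at it and no 24-week activity score can be computed.

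**3. Visit 12 read as Visit 7.** The 7-day block before a Visit 7 on day d runs from d − 7 to d − 1. The table below traces early Visit 7s through both rules. It supposes that at least 5 days were recorded in the block and, where Visit 5 was held, that it has its own activity score.

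| Visit 5 | Visit 7 | Block | Walk (day table) | Activity (Visit 7 anchor) | Activity (day table, by visit day) |
|---|---|---|---|---|---|
| none | 40 | 33–39 | 12 weeks | 24 weeks | 12 weeks |
| none | 70 | 63–69 | 12 weeks | 24 weeks | 12 weeks |
| none | 95 | 88–94 | 12 weeks | 24 weeks | 12 weeks |
| 85 | 100 | 93–99 | Visit 5 kept (0 v 15 days from day 85); Visit 7 unused | 24 weeks | Visit 5 kept; Visit 7 unused |
| 85 | 115 | 108–114 | Visit 5 kept (0 v 30); Visit 7 unused | 24 weeks | Visit 5 kept; Visit 7 unused |
| 85 | 126 | 119–125 | Visit 5 kept (0 v 41); Visit 7 unused | 24 weeks | Visit 5 kept; Visit 7 unused |
| 85 | 127 | 120–126 | 24 weeks | 24 weeks | 24 weeks |
| 85 | 140 | 133–139 | 24 weeks | 24 weeks | 24 weeks |

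The rules disagree for a Visit 7 up to day 126 and agree from day 127. FVC and the questionnaires share the walk's table.

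**4. How often this can occur.** Monitors are worn for the 7 days before planned Visits 5 and 7 and brought back at the visit. On schedule, the wear weeks are days 78–84 (85 − 7 to 85 − 1) and days 162–168 (169 − 7 to 169 − 1), with reminders at Visit 4 (day 43) and Visit 6 (day 127). A patient who stops on day 40 or 70 would usually have no device and so no score. The same holds for one who stops between Visit 5 and day 126. The likeliest case is an early-termination visit at about the time Visit 5 was due. Step 3 therefore shows where the rules part, not how often they do.

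**5. Which repair works.** Allocating each recorded day separately would split blocks. With Visit 7 on day 130, the block is days 123–129: days 123–126 (4 days) go to 12 weeks and days 127–129 (3 days) to 24 weeks. Three is below the minimum of 5, so the 24-week score is lost although the walk counts at 24 weeks. Allocating the whole block by visit day gives 130 ≥ 127, hence 24 weeks, with all 7 days kept.

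**The case against.** The strongest reply is that the two rules do different jobs: the averaging rules say which daily records make up a score, and the table says which time point the score belongs to. On that reading an early Visit 7 is windowed to 12 weeks for walk and activity alike. The reading is possible, and it is close to what the SAP should say. It is strained, however. The averaging rules attach the labels 12 weeks and 24 weeks directly to visits as held, and they use the same term for Visit 1, which has no row in either table. It also leaves Visit 12 unexplained.

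The points on rarity and reach stand. Supply of monitors makes a valid early score uncommon, and no hypothesis test or primary endpoint is involved.

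A reader might infer something stronger: that activity is simply labelled by visit while every other measure is labelled by day. The documents do not support that, because the table names the PROactive tool beside the other measures. The fault is two rules without precedence.

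**Conclusion.** The point holds as a defect of specification. Read literally, SAP 6.7 yields no 24-week activity score. With Visit 7 put in place of Visit 12 and nothing else changed, an early-termination score up to day 126 is called 24-week activity, while the same visit's walk, FVC and questionnaires are 12-week values or are not used. This rests on reading actual visit as the visit as held, and on at least 5 recorded days.

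A reader might go further and infer that the rehabilitation effect would be made to look more lasting. If a share p of 24-week scores carried an on-rehabilitation gain G and the true 24-week gain were 0, the mean gain would be p × G + (1 − p) × 0, that is 0.10 G at p = 10% and 0.30 G at p = 30%. Both values of p are assumptions, and the documents give no count of early-termination recordings. The formula also supposes that early leavers had the full gain, whereas patients who stop because of illness may have low activity, which would push the other way. Nor does the end of the trial settle p: SAP 4 says "Following termination of the trial, limited efficacy analysis will be performed for an abbreviated CTR", but not that ongoing patients were called in for an early Visit 7. Size and direction are therefore unknown. The effect is confined to descriptive secondary activity summaries.

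**What to change.** In SAP 6.7:

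- Replace Visit 12 with Visit 7 in the 24-week averaging rule.
- Keep the 7-day average before the actual visit and the 5-day minimum.
- Add one sentence: each average is allocated to 12 or 24 weeks as a single block by the study day of the visit that ends it, using the existing table (visit day 2 to 126 to 12 weeks, day 127 onward to 24 weeks) and its closest-to-planned-day tie-break.

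The visit anchor should not be deleted, since it defines which days are averaged. The cost is this wording and one programming condition, with no new data. The downside is slightly fewer 24-week activity values.
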